5.6 Evaluability

All patients who undergo ablation are evaluable for toxicity. Patients are evaluated from date of first procedure and for 30 days thereafter.

All patients who undergo ablation are evaluable for disease response provided they have had at least one disease assessment.

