Tumor Ablation in Metastatic Sarcoma Stable on Chemotherapy

**Washington University School of Medicine
Division of Oncology
[name]
[name]**

**Protocol#: 201309108
Version Date: 05/17/17**

Principal Investigator: [name] [name]., Ph.D.
[contact]
E-mail: [contact]

Sub-Investigators	Modality
[name].	Medical Oncology
[name].	Radiology
[name].	Biostatistics

Clinical Trials.gov# NCT01986829

CONFIDENTIAL

The information contained in this document is regarded as confidential and, except to the extent necessary to obtain informed consent, may not be disclosed to another party unless law or regulations require such disclosure. Persons to whom the information is disclosed must be informed that the information is confidential and may not be further disclosed by them

Tumor Ablation in Metastatic Sarcoma Stable on Chemotherapy

Protocol Revision History

Initial Approval Version	09/09/2013
Amendment #1 Version	10/06/2014
Amendment #2 Version	12/20/2016
Amendment #3 Version	05/17/2017

Tumor Ablation in Metastatic Sarcoma Stable on Chemotherapy

SCHEMA

Eligible Patients

Patients with high-grade metastatic sarcoma stable on chemotherapy for 6-12 cycles with 10 or fewer metastatic lesions which are amenable to ablation and which are measurable by CT, PET/CT, or MRI

Treatment Plan

Chemotherapy stopped at initiation of ablation therapy. All ablation therapy completed within 3 weeks with CT/PET every 9 weeks for the first year, every 12 weeks for the second year, and then every 6 months until radiographic progression or 5 years

Glossary of Abbreviations

AE	Adverse event
ALT (SGPT)	Alanine transaminase (serum glutamate pyruvic transaminase)
ANC	Absolute neutrophil count
AST (SGOT)	Aspartate transaminase (serum glutamic oxaloacetic transaminase)
BPI	Brief Pain Inventory
CBC	Complete blood count
CFR	Code of Federal Regulations
CMP	Complete metabolic panel
CR	Complete response
CRF	Case report form
CT	Computed tomography
CTCAE	Common Terminology Criteria for Adverse Events
CTEP	Cancer Therapy Evaluation Program
DOB	Date of birth
DSM	Data and Safety Monitoring
ECOG	Eastern Cooperative Oncology Group
FDA	Food and Drug Administration
HRPO	Human Research Protection Office (IRB)
INR	International normalized ratio
IR	Interventional radiology
IRB	Institutional Review Board
IULN	Institutional upper limit of normal
MRI	Magnetic resonance imaging
NCI	National Cancer Institute
NIH	National Institutes of Health

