3.0 PATIENT SELECTION

3.1 Inclusion Criteria

1. Histologically or cytologically confirmed high-grade metastatic sarcoma that has been stable on 6-12 cycles of one chemotherapeutic regimen (cytotoxic or biologic) although a change in chemotherapy is allowed if it is a result of toxicity/tolerability rather than progression. A patient must not have evidence of progression at any time while on chemotherapy in order to be eligible for this trial.
2. Measurable disease defined as lesions that can be accurately measured in at least one dimension (longest diameter to be recorded) as ≥ 10 mm with CT scan, PET CT, or MRI exam.
3. At least 18 years of age.
4. ECOG performance status ≤ 2 (Karnofsky $\geq 60\%$, see Appendix A)
5. Normal bone marrow and organ function as defined below:
 - a. Leukocytes $\geq 3,000/\text{mcl}$
 - b. Absolute neutrophil count $\geq 1,500/\text{mcl}$
 - c. Platelets $\geq 100,000/\text{mcl}$
 - d. Total bilirubin $\leq 1.5 \times \text{IULN}$ or $3 \times \text{IULN}$ with normal ALT and AST in patients with Gilbert's disease
 - e. $\text{AST(SGOT)/ALT(SGPT)} \leq 3.0 \times \text{IULN}$

- f. Creatinine less than the institutional upper limit of normal
OR
Creatinine clearance ≥ 50 mL/min/1.73 m²
 - g. INR < 1.5 or patient off Coumadin at the time of ablation
6. No more than 10 treatable lesions as evaluated by an experienced interventional oncologic radiologist for eligibility and lesion accessibility as the ablation of more than 10 lesions becomes technically infeasible. These lesions must be treated in a two- to three-week time period from initial interventional radiology evaluation. Lung and liver lesions can range from 1 cm to 7 cm for a single lesion and no greater than 5 cm for multiple lesions. There are no size criteria for the osseous lesions.
 7. The lesions will be amenable to a safe, ultrasound/computed tomographic/fluoroscopic guided percutaneous approach. The targeted metastases must be sufficiently separateable from the central nervous system, major peripheral motor nerves, bowel, and bladder. All lesions must be amenable to treatment.
 8. If patients have received radiation therapy, there must be a one-month washout period.

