5.5 Evaluation for Severity of Pain and Quality of Life

Patients will be evaluated for severity of pain using the BPI-Short Form (Appendix B) with the assistance of a study coordinator at the following time points:

- Prior to ablation
- 1 day post-ablation
- 1 month post-ablation – from first procedure if more than 1 is done
- Time of disease progression

The patients are asked to answer the questions with respect to the lesion(s) treated. They are not given a copy of the BPI-Short Form and no prior responses are available to review on subsequent visits to minimize bias. Analgesic use following the tumor ablation will be recorded as well.

Patients will be evaluated on quality of life based on the FACT-G7 survey (Appendix C) with the assistance of the study coordinator at the following time points:

- Prior to ablation
- 1 day post-ablation
- 1 month post-ablation – from first procedure if more than 1 done
- Time of disease progression

They are not given a copy of the FACT-G7 form and no prior responses are available to review on subsequent visits to minimize bias.

These surveys may be administered over the phone.

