5.9 Duration of Therapy

Tumor ablation is a one-time procedure. If at any time prior to or during ablation, the constraints of this protocol are considered to be detrimental to the patient's health and/or the patient no longer wishes to proceed with ablation, this treatment should be discontinued and the reason(s) for discontinuation documented in the case report forms.

Because the ablation procedures are intended to replace maintenance chemotherapy, chemotherapy should not resume following ablation therapy. If the treating physician feels it is warranted (i.e., the patient develops a lesion that is not amenable to ablation), then the patient will be considered to have progressed and will be taken off trial and replaced.

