6.4 Timeframe for Reporting Required Events

Reportable adverse events will be tracked for 30 days following ablation. Only AEs that are related to the ablation procedure should be reported for study data.

Deaths	
Any reportable death while on study or within 30 days of study	Immediately, within 24 hours, to PI and the IRB
Any reportable death while off study	Immediately, within 24 hours, to PI and the IRB
Adverse Events/Unanticipated Problems	
Any reportable adverse events as described in Sections 6.1.1 and 6.1.2 (other than death)	Immediately, within 24 hours to PI and within 10 working days to the IRB
All adverse events regardless of grade and attribution should be submitted cumulatively	Include in DSM report
Noncompliance and Serious Noncompliance	
All noncompliance and serious noncompliance as described in Sections 6.1.6 and 6.1.7	Immediately, within 24 hours, to PI and within 10 working days to the IRB

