7.0 STUDY CALENDAR

Baseline evaluations are to be conducted within 3 weeks prior to start of protocol therapy. Scans and x-rays must be done no more than 3 weeks prior to the start of ablation.

	Baseline	Ablation	1 day after ablation	1 month after ablation	Follow-up ^d	Progression
Physical exam, incl. medical history, weight, VS, PS	X					
CBC	X					
CMP	X					
PT/PTT and INR	X					
Pregnancy test ^a	X					
IR evaluation ^b	X					
CT or PET scan					X ^d	
FACT-G7	X		X	X		X
BPI short form	X		X	X		X
Adverse events		X ^c				
Survival follow-up						X ^e

a: Women of childbearing potential only

b: Patients must have 10 or fewer treatable lesions when enrolled in the study and will be seen in consultation by an experienced interventional oncologic radiologist with evaluation of available PET, CT, MR, and US images for eligibility and lesion accessibility

c: Tracked for 30 days following ablation

d: The patients will be imaged as per routine care at the following time points: 6 weeks post first-procedure, every 9 weeks for the first year, every 12 weeks for the second year, and every 6 months for 5 years or until death or radiographic progression, whichever comes first.

e. After progression, patients will be followed every 3 months for survival only.

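### The 30-day toxicity window is tied to the first procedure in Section 5.6 and to an unspecified one elsewhere, so follow-up after the last staged ablation may be short

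*Combined protocol and SAP*

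**What the plan says.** - **Toxicity window.** Section 5.6 makes every ablated patient evaluable for toxicity and adds: "Patients are evaluated from date of first procedure and for 30 days thereafter". It is the only text on the toxicity window that names a particular procedure as its start.
- **Other statements of the window.** Section 6.4 says "Reportable adverse events will be tracked for 30 days following ablation". Footnote c of the Section 7.0 calendar says "Tracked for 30 days following ablation". The Section 8.0 schedule makes the Toxicity Form due 30 days after ablation. None of the three says first or last procedure.
- **Staging.** The Schema has "All ablation therapy completed within 3 weeks", with no stated start for the 3 weeks. Section 3.1 item 6 admits patients with "No more than 10 treatable lesions as evaluated by an experienced interventional oncologic radiologist" and continues "These lesions must be treated in a two- to three-week time period from initial interventional radiology evaluation". Section 5.5 provides for several procedures when it times a pain and quality-of-life assessment at "1 month post-ablation – from first procedure if more than 1 is done".
- **Text pointing the other way.** Section 5.9 states "Tumor ablation is a one-time procedure".
- **What is recorded.** Sections 6.1.1 and 6.4 limit adverse events in the study data to those related to the ablation procedure.

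**The concern.** Each ablation carries its own procedural risk. A window that opens and closes relative to the first one gives later procedures less observation time, and the longer the staging, the less they get. A related complication of a late procedure can then fall outside the study data, although the same complication at the same interval after a single-session ablation would be counted.

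There is also a consistency problem. If the wording in Sections 6.4, 7.0 and 8.0 means the last procedure, it contradicts Section 5.6. Two people abstracting the same staged patient could then record different events, each following the protocol. What is at stake is the completeness of the toxicity summary that Section 10.0 requires for the monitoring committee, and of any complication rate reported from the trial.

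**Working it through.** The plan states no follow-up time after the last procedure, so there is no figure of its own to reproduce. It has to be derived.

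**Inputs**
- Window W = 30 days from the first procedure (Section 5.6).
- Longest period for all ablation = 3 weeks = 21 days (Schema). Section 3.1 item 6 gives 14 to 21 days, counted from the initial interventional radiology evaluation.
- More than one procedure is foreseen (Section 5.5).

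**Step 1: follow-up after the last procedure.** Let S be the days from first to last procedure.
- First-procedure anchor: follow-up after the last procedure = W − S.
- Last-procedure anchor: follow-up after the last procedure = 30 days, and total observation from the first = 30 + S.

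| S (days) | After last procedure, first anchor | Total from first procedure, last anchor |
|---|---|---|
| 0 | 30 − 0 = 30 | 30 + 0 = 30 |
| 7 | 30 − 7 = 23 | 30 + 7 = 37 |
| 14 | 30 − 14 = 16 | 30 + 14 = 44 |
| 21 | 30 − 21 = 9 | 30 + 21 = 51 |

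**Step 2: the clock in Section 3.1 item 6.** Let g be the days from the radiology evaluation to the first procedure. With a 21-day limit, S is at most 21 − g, so follow-up after the last procedure is at least 30 − (21 − g) = 9 + g days. It is 9 only if the first procedure falls on the day of the evaluation (g = 0) and the last on day 21. With an assumed gap of g = 7 it is at least 16 days. The documents give no value for g.

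**Step 3: do the wordings give different counts?** Take a patient treated on days 0 and 21 with a non-fatal related complication on day 35, which is 35 − 21 = 14 days after the second procedure. Under Section 5.6 the window closed on day 30 and the event is not counted. If the other three places mean the last procedure, the window closes on day 21 + 30 = 51 and the event is counted.

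**Step 4: can the unspecified wording be resolved from the text?** No.
- Section 5.5 counts its one-month post-ablation point from the first procedure, which favours a first anchor.
- Section 9.1 counts the scan at about 6 weeks from the last procedure, while calendar footnote d counts the 6-week scan from the first. The protocol uses both anchors, so neither can be assumed where none is named.

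**The case against.** The strongest reply is that Section 5.6 concerns evaluability, while the operational rules for adverse events sit in Sections 6.4, 7.0 and 8.0. Those can be read as 30 days after the whole course of ablation. Section 5.9 speaks of ablation as a single undertaking, and Section 5.5 adds an explicit qualifier when it wants the first procedure. On that reading three of the four places already give full follow-up. This is a fair reading, and it means that 9 days is not an established property of the trial. It does not remove the problem, because Section 5.6 would then contradict the other three.

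Three stronger readings are tempting, and the documents do not support them.

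- **Staged patients typically get about 9 days.** That figure is the extreme. Step 2 shows that any gap between the radiology evaluation and the first procedure lengthens it. The blood-thinner and clopidogrel interruption of 5 to 7 days in Section 5.7 could create such a gap in some patients.
- **The complication rate is biased low where risk is highest.** This would need the share of staged patients, the timing of complications, and a link between number of lesions, number of sessions and risk. None is given. Several lesions might be treated in one session, and if complications appear within days, little is lost.
- **Serious harm after day 30 goes unseen.** Section 6.4 covers reportable deaths on and off study. Section 6.2 sets no 30-day limit on unanticipated problems. Section 10.0 requires ongoing monitoring for serious toxicities, and Section 5.10 follows patients removed for unacceptable events until resolution or stabilization. These do not replace routine collection of non-fatal related events, so that part of the concern stands.

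It is also true that toxicity is neither a primary nor a secondary objective in Section 2.0, and that Section 11.2 plans no analysis of it.

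**Conclusion.** The point holds as an unreconciled anchor with a possible loss of safety data. Followed literally, Section 5.6 leaves 30 days minus the first-to-last span after the last procedure: 16 days for a 14-day span and 9 days at the 21-day limit. This assumes that the 3-week limit is kept. Section 5.4 allows postponement, but the documents do not say that a postponed session may go beyond 3 weeks, so no shorter figure is claimed. Single-session patients are not affected.

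Non-fatal related events after later procedures may be missed in staged patients, and the wordings can yield different counts. Any effect of the first-procedure anchor on the count would be towards fewer events, but its size cannot be derived, and it could be negligible. The 3-month progression-free rate and the sample size of 36 do not depend on this window. The wording should be amended, but the defect does not threaten the trial's main conclusion.

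**What to change.** State one adverse event collection window and use the same words in Section 5.6, Section 6.4, calendar footnote c and the Section 8.0 Toxicity Form schedule: *from the date of the first procedure until 30 days after the last ablation procedure*. Every patient then has 30 days of observation after the last procedure.

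The cost is a wording amendment and at most 51 − 30 = 21 more days of event collection, in staged patients only. The one-month survey contact is counted from the first procedure, so an additional contact may be needed to close the longer window. If any staged patients have already been closed out 30 days after their first procedure, the report should give their number and state which window was applied. Treatment, the primary endpoint and the sample size are unchanged.

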2.0 OBJECTIVES

2.1 Primary Objectives

To determine the progression-free rate at 3 months in patients with metastatic sarcoma stable on chemotherapy whose lesions have undergone ablation. PFR is defined as the percentage of patients with no progression (local recurrence of an ablated lesion or the appearance of a new lesion) at 3 months after ablation.

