9.0 MEASUREMENT OF EFFECT

9.1 Antitumor Effect – Solid Tumors

There will be another PET/CT at 42 +/- 3 days following the last procedure (approximately 6 weeks post-procedure) and one every 9 weeks thereafter until progression of disease. All imaging is standard of care.

For the purposes of this study, patients should be re-evaluated for response every 9 weeks. In addition to a baseline scan, confirmatory scans should also be obtained 4 weeks (not less than 4) weeks following initial documentation of objective response.

Response and progression will be evaluated in this study using the new international criteria proposed by the revised Response Evaluation Criteria in Solid Tumors (RECIST) guideline (version 1.1) [Eur J Ca 45:228-247, 2009]. Changes in the largest diameter (unidimensional measurement) of the tumor lesions and the shortest diameter in the case of malignant lymph nodes are used in the RECIST criteria.

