9.4.3 Evaluation of Best Overall Response

The best overall response is the best response recorded from the start of the treatment until disease progression/recurrence (taking as reference for progressive disease the smallest measurements recorded since the treatment started). The patient's best response assignment will depend on the achievement of both measurement and confirmation criteria.

For Patients with Measurable Disease (i.e., Target Disease)

Target Lesions	Non-Target Lesions	New Lesions	Overall Response	Best Overall Response when Confirmation is Required*
CR	CR	No	CR	>4 wks. Confirmation**
CR	Non-CR/Non-PD	No	PR	>4 wks. Confirmation**
CR	Not evaluated	No	PR	
PR	Non-CR/Non-PD/not evaluated	No	PR	
SD	Non-CR/Non-PD/not evaluated	No	SD	Documented at least once >4 wks. from baseline**
PD	Any	Yes or No	PD	no prior SD, PR or CR
Any	PD***	Yes or No	PD	
Any	Any	Yes	PD	

* See RECIST 1.1 manuscript for further details on what is evidence of a new lesion. ** Only for non-randomized trials with response as primary endpoint. *** In exceptional circumstances, unequivocal progression in non-target lesions may be accepted as disease progression. Note: Patients with a global deterioration of health status requiring discontinuation of treatment without objective evidence of disease progression at that time should be reported as “symptomatic deterioration.” Every effort should be made to document the objective progression even after discontinuation of treatment.
				

For Patients with Non-Measurable Disease (i.e., Non-Target Disease)

Non-Target Lesions	New Lesions	Overall Response
CR	No	CR
Non-CR/non-PD	No	Non-CR/non-PD*
Not all evaluated	No	not evaluated
Unequivocal PD	Yes or No	PD
Any	Yes	PD
* 'Non-CR/non-PD' is preferred over 'stable disease' for non-target disease since SD is increasingly used as an endpoint for assessment of efficacy in some trials so to assign this category when no lesions can be measured is not advised		

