9.4.5 Other Definitions

Progression-free rate: PFR is defined as the percentage of patients with no progression (local recurrence of an ablated lesion or the appearance of a new lesion) at 3 months after ablation.

Overall survival: OS is defined as the time from diagnosis of metastatic disease to the time of death.

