11.0 STATISTICAL CONSIDERATIONS

11.1 Power

Our power analysis is based on the following hypotheses. The null hypothesis assumes that the 3-month progression-free survival (PFS) for treatment with ablation therapy is

overall 20% for patients with metastatic sarcoma. We hypothesize in the alternative hypothesis that the 3-month PFS will be at least 40% with ablation therapy. This is based on data from a clinical trials database used to provide reference values for conducting phase II studies in sarcoma with PFR as the principal endpoint (5). An enrollment of 36 patients can achieve at least 80% power to conclude that the alternative hypothesis is true based on a two-sided test of one-sample proportion at a significance level of 0.05.

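### On its natural reading, Section 5.6 drops ablated patients who die or deteriorate before their first scan from the 3-month PFR, and no other rule counts them as failures

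*Combined protocol and SAP*

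**What the plan says.** Section 5.6 gives two evaluability rules side by side. For safety, "All patients who undergo ablation are evaluable for toxicity", with no further condition. For efficacy, "All patients who undergo ablation are evaluable for disease response provided they have had at least one disease assessment". It does not say whether the assessment must follow ablation, or which endpoints the second rule governs.

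Section 2.1 gives this definition of the primary endpoint: "percentage of patients with no progression (local recurrence of an ablated lesion or the appearance of a new lesion) at 3 months after ablation"; Section 9.4.5 repeats the definition. Neither lists death or clinical decline as a failure.

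On the first scan, Section 9.1 says "There will be another PET/CT at 42 +/- 3 days following the last procedure", whereas footnote d of the Section 7.0 calendar places it 6 weeks after the first procedure. The schema allows 3 weeks to complete all ablation.

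A note to the table in Section 9.4.3 says: "Patients with a global deterioration of health status requiring discontinuation of treatment without objective evidence of disease progression at that time should be reported" under a separate label, symptomatic deterioration, and not as progressive disease.

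Section 11.1 tests a null 3-month rate of "overall 20% for patients with metastatic sarcoma" against an alternative of at least 40%, with 36 patients enrolled. Section 11.2 plans a Kaplan-Meier estimate of 3-month PFS. Section 11 names no analysis set, no censoring rule, and no rule for patients whose 3-month status is unknown.

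**The concern.** The efficacy rule makes inclusion depend on something that happens after treatment: staying alive and well enough to be scanned. The unconditional safety rule beside it suggests that the added condition is meant to exclude someone.

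A death or clinical decline before the first scan is an unfavourable outcome. Removing such a patient takes one from the denominator and none from the numerator, so the rate can only rise. In a single-arm trial with a fixed benchmark, no control group shares the distortion. With 36 patients, a few exclusions can decide the test.

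Adding death to the definition of progression would not by itself cure this, because a patient already excluded under Section 5.6 is not in the set to which the definition is applied.

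**Working it through.** **Inputs.** Null rate 0.20, alternative 0.40, two-sided 0.05, N = 36 (Section 11.1). First scan at about 6 weeks (Sections 7.0 and 9.1). The number k of ablated patients lost before a post-ablation scan is an assumption, shown over a range; all k are taken to be failures.

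**1. The plan's own figure.** n = [(1.960·√(0.20·0.80) + 0.842·√(0.40·0.60)) / 0.20]² = 35.78, rounded up to 36; normal-approximation power is 80.2%. The stated size reproduces. It has no allowance for non-evaluable patients.

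**2. Exposure time.** Taking 3 months as 13 weeks, a first scan at week 6 means 6/13 = 46% of the window passes before a patient can qualify.

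**3. Shift in the rate.** Rate among evaluable patients = true all-ablated rate × 36/(36 − k).

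| k | evaluable | true 20% becomes | true 40% becomes |
|---|---|---|---|
| 0 | 36 | 20.0% | 40.0% |
| 2 | 34 | 21.2% | 42.4% |
| 3 | 33 | 21.8% | 43.6% |
| 4 | 32 | 22.5% | 45.0% |
| 6 | 30 | 24.0% | 48.0% |

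**4. Effect on the test.** Score z = (x/n − 0.20)/√(0.16/n). The plan does not say whether its one-sample test is a score or an exact test, so both are shown. The exact p is given by the minimum-likelihood method and by doubling the upper tail.

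| result | rate | z | exact p | doubled tail |
|---|---|---|---|---|
| 11/36 | 30.6% | 1.58 | 0.141 | 0.178 |
| 11/33 | 33.3% | 1.91 | 0.078 | 0.102 |
| 11/32 | 34.4% | 2.03 | 0.048 | 0.082 |
| 12/36 | 33.3% | 2.00 | 0.058 | 0.085 |
| 12/33 | 36.4% | 2.35 | 0.027 | 0.043 |

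Three losses turn 12 successes from non-significant to significant by either exact method; by the score test 12/36 is already significant. Four losses do the same for 11 successes by the score test and the minimum-likelihood exact test, but not with the doubled tail. One loss changes no decision under any of the three: the smallest significant count is 12 (score) or 13 (both exact versions) at both n = 36 and n = 35.

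**5. False-positive risk.** Suppose the true all-ablated rate is 20% and 36 are ablated. With the score test, the chance of an upper-tail rejection is 0.042 with no losses (cut-off 12/36) and 0.085 with four (cut-off 11/32). With the doubled-tail exact test it is 0.018 with none (13/36) and 0.040 with three (12/33).

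**6. Are such losses conceivable?** Section 1.1 gives a 12-month median survival in metastatic disease. A constant hazard would give 1 − 0.5^(6/52) = 7.7% deaths by week 6, or 0.077 × 36 = 2.8 patients. This is probably too high for patients selected as stable with ECOG ≤ 2. It shows only the order of magnitude.

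**The case against.** The strongest reply is that the exclusion is not written into the primary endpoint. Section 5.6 speaks of disease response, while Section 9.1 names response and progression separately. Sections 2.1 and 11.2 describe the population simply as those treated with ablation. Moreover, a baseline scan is itself a disease assessment, and every eligible patient has one; read literally, the rule excludes nobody. All this stands, and it is why the point is conditional. But if Section 5.6 does not govern the PFR, nothing says how a patient without a post-ablation scan is counted, and the same clarification is needed.

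Other provisions might seem to recover these patients. Section 5.9 deems a patient who resumes chemotherapy to have progressed, but also has that patient replaced, and it does not reach deaths or declines without chemotherapy. The note in Section 9.4.3 asks for efforts to document progression later; that helps only patients who live to be imaged.

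A reader might also infer more than the documents support:

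- That Kaplan-Meier would censor unscanned patients at time zero. No censoring rule is given, and Section 11 calls the endpoint PFS, which ordinarily counts death, although the stated definition does not.
- That up to 9 of 13 weeks (69%) pass before evaluability. This requires the scan to be timed from the last procedure, as in Section 9.1, and the endpoint from the first. Section 7.0 times the scan from the first procedure.
- That one exclusion matters because 14/36 = 38.9% becomes 14/35 = 40.0%. The 40% is the hypothesised rate, not the test boundary; 14/36 already gives z = 2.83 against 20%.
- That everyone lost is failing. For administrative losses the direction of bias is unknown.

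**Conclusion.** The concern holds in conditional form. If the disease assessment in Section 5.6 means one after ablation, and if the rule sets the primary denominator, patients who die or deteriorate before the first scan are omitted and the 3-month PFR is biased upward. Both conditions are reasonable readings, but neither is stated, so the plan cannot be said to prescribe the exclusion. Left open, the denominator could be chosen after the results are known.

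The size rests entirely on early losses that the plan does not project. It is zero with no losses. With two to four lost failures among 36, a true 40% would appear as 42.4% to 45.0%. Three or four losses can reverse a borderline test result, depending on which version of the test is used; a single loss cannot. The comparison also takes the 20% reference to apply to all treated patients, which the plan does not state.

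**What to change.** In Sections 5.6 and 11.2:

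- State that the 3-month PFR denominator is every patient who starts at least one ablation procedure, including any later replaced under Section 5.9.
- State that death, symptomatic deterioration or the start of other anticancer treatment before a post-ablation assessment counts as not progression-free.
- Count patients unassessed for purely administrative reasons as not progression-free as well, and report the evaluable-only rate as a sensitivity analysis. This step is a conservative convention that may understate the rate; it does not correct an error.
- If an evaluable set is kept, say that its disease assessment must follow ablation, and reconcile the first-scan timing in Sections 7.0 and 9.1.

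The cost is a few sentences and possibly a slightly lower reported rate. The change alters only the analysis and needs no extra procedures. N = 36 stands if 40% was meant for all ablated patients. If it was meant only for assessed patients, a 10% early loss (an assumption) makes the all-ablated rate 0.40 × 0.90 = 36%. By the formula in step 1, power at 36 is then about 64%, and 80% power would need 56. The sponsor should therefore say which population the 40% describes.
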